vaccination with Cox-2 inhibition.⁷⁸⁻⁸⁰ Recent literature has suggested increased risk of adverse cardiovascular events associated with the administration of some selective Cox -2 inhibitors.⁸¹⁻⁸³ The literature regarding the precise risk with celecoxib remains controversial, with the reported cardiovascular side effects observed in its long-term users. This trial will involve a short course of celecoxib; given at an oral dose of 200 mg daily starting on the day of discharge from surgery and continuing until the off-study treatment visit. The dose will be 200 mg, twice a day, the day of vaccination (Monday) and over the 4 days of chemokine modulation regimen (Tuesday-Friday). It has been suggested that lower doses and shorter length of administration decrease the risk of adverse cardiovascular events associated with administration of celecoxib.

Poly-I:C (polyinosinic-polycytidyllic acid) is a small molecule ligand (mimicking double-stranded RNA ligand of Toll-Like Receptor 3 [TLR3],^{84,85} extensively tested as a single drug in the setting of infectious diseases and cancer. It has been shown that TLR3 is involved in the recognition of viral components, such as poly-I:C and dsRNA. In contrast, TLR7 and TLR8 appear to recognize ssRNA viruses and ssRNA, respectively.⁸⁶ It is also noted that IFN- α , β and/or γ treatment of cells results in the remarkable enhancement of TLR3 expression levels, and that poly-I:C is capable of inducing the production of pro-inflammatory cytokines (IL-6 and TNF α) and chemokines (CCL2/MCP-1, CCL5/RANTES, CCL20/MIP-3 α , and CXCL10/IP-10). Other TLR ligands, such as LPS, lipoteichoic acid, peptidoglycan, flagellin, and CpG, failed to exert similar effects. These reports, in addition to our preclinical data, provide strong rationale for the combined use of poly-IC and IFN α . With regard to clinical use of poly-I:C in cancer patients, it has been shown that low dose of poly-I:C is more efficacious than a high dose for enhancing immune effects, and that higher doses actually inhibit a number of cell-associated immune functions. Rintatolimod (Ampligen) is a poly-IC derivative with reduced half-life in vivo and increased selectivity of binding to TLR3.

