5.1 Phase 1: Dose assessment of α DC1 vaccine chemokine-modulatory regimen (CKM)

The recommended Phase 2 dose of the combination of α DC1 vaccine in combination with IFN α , rintatolimod, and celecoxib will be established by administering fixed doses of the vaccine, rintatolimod, and celecoxib in combination with escalating doses of IFN α . Patients will receive a priming dose of the vaccine which consists of 1 intranodal injection followed by 1 intradermal injection on the Monday of the first week. Patients will then receive a booster dose of the DC vaccine, which consists of 1 intranodal injection and 1 intradermal injection, on Monday followed by the CKM regimen on days Tuesday through Friday of the booster cycle.

There will be 3 dose finding cohorts with one additional de-escalation cohort (designated -1) if needed, as shown in the table below:

Phase 1 Dose Tiers	α DC1 Vaccine (IN + ID)***	Components of CKM cycle		
		IFN α (MU/M ² IV) Days T-F	Rintatolimod* (mg, IV) Days W&F	Celecoxib** (mg, orally, twice a day) Days T-F
-1	3+3 M cells	5	100	200
1	3+3 M cells	5	200	200
2	3+3 M cells	10	200	200
3	3+3 M cells	20	200	200

*Rintatolimod starting dose will be 200 mg unless dose escalation is from tier -1 in which case cohorts 2 and 3 will use 100 mg of rintatolimod.

**Celecoxib will be administered orally, at a dose of 200 mg, once a day starting the day of the first vaccine (day 1 of week 1) and continue until Friday the last day of the CKM regimen. The dose will be increased to 200 mg, twice a day on the days of vaccination (Monday) and over the 4 days of chemokine modulation regimen (Tuesday - Friday).

***In case of limited availability of vaccine, the treatment may proceed with reduced numbers of the cells (down to 0.5 M IN + 0.5 M ID for each vaccination cycle).

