- Greater than or equal to grade 3 non-hematologic adverse events, except for the following grade 3 toxicities unless they last greater than one week:
 - Flu-like symptoms/constitutional symptoms (i.e., fever, chills, arthralgias, myalgias)
 - Depression, anxiety, restlessness, or insomnia
 - Manageable GI symptoms (i.e., nausea, diarrhea)

The observation period for each patient in the Phase 1 portion of this study will be up to 5 weeks (i.e. up to and including the Friday 1 week after the end of the chemokine modulating regimen).

Note: The last 2 patients in the Phase 1 cohort that determines the RP2D will continue on to the Phase 2 part of the trial and will receive the 2nd and 3rd booster/CKM cycles and follow-up per the Phase 2 portion of this protocol. All patients in the dose finding cohort will be followed for primary efficacy endpoints as well as have blood and serum drawn for corollary studies.

Patients in the Phase 1 (safety) cohort will receive their study treatment and will be monitored for RLTs according to the following timeline:

Eligibility	ECOG performance status, blood work CRS + HIPEC
Screening	History and physical exam, ECOG performance status, blood work, and evaluation of tumor material
Post-surgery (after the discharge from the hospital)	Leukapheresis
Week 1* (upon recovery from surgery; at least 4 weeks after surgery)	Priming Vaccine dose; no chemokine modulation Monday: α DC1 vaccine Oral celecoxib, 200 mg, twice daily on the day of vaccination Tues – Sun: oral celecoxib 200mg, once daily
Weeks 2-3	Rest – continue oral celecoxib, 200 mg, once daily
Week 4	Cycle 1 (“booster cycle”) Monday: α DC1 vaccine Tues – Fri: Systemic Chemokine Modulation Regimen. Oral celecoxib, 200 mg, twice daily on the days of vaccination and CKM. Celecoxib will be discontinued after CKM on Friday. Rintatolimod is only administered on Wednesday and Friday.
Off study treatment	Follow-up for Time-to-Progression/occurrence (TTP)

CRS: Cytoreductive surgery; HIPEC: Hyperthermic intraperitoneal chemoperfusion; TTP: Time-to-progression

*Adjuvant immunotherapy may be delayed until full recovery at the discretion of the investigator/sub-investigator. The beginning of immunotherapy will be considered week 1 of the experimental treatment and the timing of all subsequent elements of treatment will be based upon the first vaccine.

5.2 Phase 2: Efficacy assessment of α DC1 vaccine followed by the chemokine-modulatory regimen (CKM)

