5.4 Agent Administration

5.4.1 Celecoxib

The drug will be administered orally, at a dose of 200 mg, twice daily on all study treatment days only.

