10. STUDY CALENDAR

Baseline/screening evaluations will be conducted within 14 days and imaging will be conducted within 28 days of leukapheresis.

There is a window of ± 1 week available for scheduling treatment and/or procedures at the discretion of the Investigator/Sub-investigator. This applies also if a course is missed or a subject's treatment and/or testing day(s) need to be rescheduled due to the subject's inability to comply with the study calendar (i.e., hospitalizations, business, vacation plans, travel from long distances for study treatment, in advance of the scheduled date to allow ready access to the result(s), reduce financial burden on the subject [i.e. non-UPMC insurance coverage] or reduce travel inconvenience, illness, transportation issues, holidays, family emergencies, etc.).

Parameter	Eligibility	Surgery	Screening	Week 1* (Priming)	Week 4* (Booster Cycle 1)	Week 8* (Booster Cycle 2)	Week 12* (Booster Cycle 3)	Off treatment visit ⁹
Informed Consent	X							
History and Physical Exam ¹			X	X	X	X	X	
Vital Signs ²			X	X	X	X	X	
Adverse Event/Con Meds ¹⁰			X	X	X	X	X	X
ECOG Performance Status			X	X	X	X	X	
CEA			X					X
Urine pregnancy test ³			X	X ³				
CT or MR imaging (scheduled as clinically indicated)			X ⁸			X		X
CBC, platelets, differential ⁷			X	X	X	X	X	
Chemistries ^{4,7}			X	X	X	X	X	
Leukapheresis			X					
α DC1 vaccine				X	Monday	Monday	Monday	
Chemokine modulation					Tues-Fri	Tue-Fri	Tue-Fri	
Celecoxib ⁵				X	M-F	M-F	M-F	
Blood (60 cc) in vitro assays ⁶				X	X	X	X	
Tissue collection		X						

*. The indicated weeks represent "target weeks" In order to avoid conflict with chemotherapy, each cycle of immunotherapy can be delayed: *see the study schema*).

1. Physical examination will be performed by the investigator/sub-investigator or their designee.
2. Vital signs (temperature, blood pressure, pulse rate, and respiratory rate) will be performed before (within 30 minutes) and after (within 30 minutes) intra-nodal vaccine doses.
3. Pregnancy test is only for WOCBP who are sexually active. Test prior to cycle 1 is to be done on day 1 and must be resulted prior to vaccination.
4. Glucose, BUN, creatinine, sodium, potassium, chloride, CO₂, calcium, total protein, albumin, alkaline phosphatase, AST, ALT, total bilirubin, amylase, lipase.
5. Celecoxib will be administered orally, at a dose of 200 mg, twice daily on vaccine and CKM study treatment days

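### Celecoxib dosing contradicts itself: Phase 1 is 26 or 6 days depending on the section, and Section 2.6.2 describes continuous daily use that the Phase 2 treatment sections do not

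*Combined protocol and SAP*

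**What the plan says.** Three celecoxib schedules stand in the current text of the combined protocol and SAP.

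- **Section 2.6.2**, speaking of what this trial will do: celecoxib is given at 200 mg daily, "starting on the day of discharge from surgery and continuing until the off-study treatment visit". On treatment days, "The dose will be 200 mg, twice a day, the day of vaccination (Monday) and over the 4 days of chemokine modulation regimen". The same passage calls this a short course and notes that lower doses and shorter use have been suggested to reduce cardiovascular risk.
- **Section 5.1 (Phase 1)**: the dose-table footnote gives 200 mg "once a day starting the day of the first vaccine (day 1 of week 1) and continue until Friday" of the CKM week, rising to twice a day on vaccine and CKM days. The Phase 1 timeline repeats this for rest weeks 2-3: "continue oral celecoxib, 200 mg, once daily".
- **Section 5.4.1**, with no phase named: "The drug will be administered orally, at a dose of 200 mg, twice daily on all study treatment days only". Footnote 5 of the Section 10 calendar, also with no phase named, reads: "Celecoxib will be administered orally, at a dose of 200 mg, twice daily on vaccine and CKM study treatment days". The Section 5.2 table for Phase 2 fits this rule. It gives two doses on the priming day and none in the rest weeks, stops celecoxib after each CKM Friday and, at booster cycle 2, expressly reintroduces it. The Schema fits it for the five days of each booster cycle.

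No passage says which rule prevails, or that the two phases are meant to differ.

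**The concern.** Celecoxib is one of the three CKM drugs, so its schedule is part of the regimen under test.

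In Phase 1, two rules inside the treatment plan itself conflict, and a site cannot comply with both. A patient's exposure then depends on which page was read.

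In Phase 2, the treatment sections are consistent, but the rationale describes something much longer. That matters for two reasons. First, the cardiovascular reassurance in 2.6.2 rests on brevity, while the schedule beside it is the longest in the document. Second, Section 7 separates immunotherapy from adjuvant chemotherapy by a wash-out of at least 5 days and limits toxicity data to the immunotherapy periods. Celecoxib given continuously, as 2.6.2 has it, would run through the intervals that are not covered.

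**Working it through.** The documents state no total number of celecoxib days and no cumulative dose, so there is no stated figure to reproduce. The totals below are calendar counts.

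**Inputs.** A twice-daily day is 400 mg and a once-daily day is 200 mg. Phase 1 has one priming day and one 5-day booster cycle, in weeks 1 and 4 (5.1). Phase 2 has one priming day and three 5-day booster cycles (5.2). The calendar places these in weeks 1, 4, 8 and 12, while the timing list in 5.2 gives three intervals with a target of 4 weeks. The off-treatment visit is 1-2 weeks after the last treatment day, but its procedures may be done on the last CKM day (5.8), so 0-14 days are added. Priming is assumed to fall on a Monday.

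**Phase 1**

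- 5.4.1 and the calendar: 1 + 5 = 6 days; 6 × 400 = 2,400 mg.
- 5.1: Monday of week 1 to Friday of week 4 is 3 × 7 + 5 = 26 days, of which 6 are twice daily and 20 once daily; 6 × 400 + 20 × 200 = 6,400 mg.
- 2.6.2, which names no phase: 26 days from priming, plus 0-14 days to the off-treatment visit, gives 26-40 days, plus the time from discharge to priming.

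**Phase 2, treatment days only (5.2, 5.4.1, calendar)**

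- 1 + 3 × 5 = 16 days; 16 × 400 = 6,400 mg.

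**Phase 2, rule in 2.6.2, counted from priming alone.** With n days in total, the dose is 16 × 400 + (n − 16) × 200 mg.

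- Calendar weeks 1 to 12: 11 × 7 + 5 = 82 days, or 6,400 + 66 × 200 = 19,600 mg. With 14 days added: 96 days, or 6,400 + 80 × 200 = 22,400 mg.
- Three 4-week intervals: 12 × 7 + 5 = 89 days, or 6,400 + 73 × 200 = 21,000 mg. With 14 days added: 103 days, or 6,400 + 87 × 200 = 23,800 mg.
- Against 16 days and 6,400 mg, the smallest of these is 82/16 = 5.1 times the days and 19,600/6,400 = 3.1 times the dose.

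**Phase 2, rule in 2.6.2, counted from discharge.** The documents give no discharge date. Assuming discharge 1-4 weeks after surgery, n = 7 × (weeks from surgery to priming + sum of booster intervals) + 5 + (0 to 14) − 7 × (weeks from surgery to discharge).

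- Target timing (priming at week 8, 4-week intervals): 7 × 20 + 5 = 145; lowest 145 − 28 = 117, highest 145 + 14 − 7 = 152 days; 26,600-33,600 mg.
- Shortest permitted timing (week 6, 4-week intervals): 7 × 18 + 5 = 131; 103-138 days.
- Longest permitted timing (week 16, 12-week intervals): 7 × 52 + 5 = 369; 341-376 days; 71,400-78,400 mg.

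**The case against.** The best defence is that 2.6.2 is background, and that the sections a site would use for Phase 2 all give the same 16 days. That stands. A reader might infer that the Phase 2 regimen is undefined, but the documents do not support this: the months-long reading rests on 2.6.2 alone. It does not remove the point, because 2.6.2 is worded as a statement about this trial and carries the safety argument for the drug.

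The defence does not reach Phase 1, where both conflicting rules are in Section 5. Nor does it help to count the celecoxib-only rest days as study treatment days. Section 5.4.1 would then require twice-daily dosing on days when 5.1 gives once-daily dosing.

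A reader might also infer that the Phase 1 toxicity data do not describe the Phase 2 regimen. That goes too far. It requires 5.1 to govern, which is the open question. Even then, dosing on vaccine and CKM days is identical in both phases, and Phase 1 only adds once-daily dosing between priming and booster. Total celecoxib would be 6,400 mg in each phase. Interferon is the escalated drug, and Phase 2 has its own continuous toxicity monitoring (13.4).

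The Tuesday-to-Friday heading in the Phase 1 dose table may look like a further conflict. It is not: it sits under the components of the CKM cycle, and its own footnote supplies the other days.

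Finally, short course may be meant relative to the long-term users mentioned in 2.6.2. That softens the tension at target timing, but is hard to sustain at the longest permitted timing.

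**Conclusion.** The contradiction is real and is in current text.

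- **Phase 1:** 5.1 and 5.4.1 cannot both be followed. The difference is 26 against 6 days, and 6,400 against 2,400 mg. These counts need only the 5.1 timeline.
- **Phase 2:** the treatment sections are consistent at 16 days and 6,400 mg, but 2.6.2 describes at least 82 days from priming on the calendar weeks, or 89 with three 4-week intervals. To this come 0-14 days to the off-treatment visit and the time from discharge to priming. The 117-152 days at target timing rest on the assumed discharge 1-4 weeks after surgery.

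If 5.1 governs Phase 1, the celecoxib pattern between cycles differs between the phases without explanation; nothing stronger follows for the recommended Phase 2 dose. A difference in cardiovascular risk might also be inferred, but it cannot be calculated, because the documents give no event rate for either schedule in this trial. Sample size, alpha and power are unaffected. The point merits correction as an inconsistency in the text that governs drug exposure and safety collection. It is not a flaw in the analysis.

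**What to change.** Reconcile the Schema, Section 2.6.2, the Section 5.1 dose-table footnote and timeline, the Section 5.2 table, Section 5.4.1 and calendar footnote 5 into one stated celecoxib schedule for each phase. State whether the two schedules are meant to differ and, if so, why. Name the phase or phases to which 5.4.1 and the calendar footnote apply. Align the short-course statement in 2.6.2 with the schedule adopted. If that schedule includes dosing between cycles, say how Section 7 collects toxicity data over those days. Which schedule to adopt is for the sponsor. The cost is a wording amendment, with no change to sample size or analysis.

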2.6.3 Clinical experience with chemokine modulating regimen (CKM)

In 2012, we completed an Expanded Access - single patient IND (BB-IND 14, 934) protocol utilizing the CKM regimen of IFN intravenously at 5 MU/m², rintatolimod intravenously at 200 mg, and celecoxib orally at 200 mg twice a day. This regimen was well tolerated in this patient with grade 3 flushing and hypotension that resolved with slowing of the rintatolimod administration rate on the first cycle.

Similar CKM treatment is currently being evaluated in a Phase 1/2 clinical trial, UPCI 10-131 (IND 112532), open for patients with resectable, metastatic, colon cancer. In that trial, rintatolimod is administered daily and not every second day, as in the current trial. This trial evaluates the CKM regimen of IFN intravenously (dose escalation of 5, 10, and 20 MU/m²), rintatolimod intravenously at 200 mg, and celecoxib orally at 200 mg twice a day. Treatment on phase I has been completed without any regimen limiting toxicities and current enrollment is to Phase 2 portion of the clinical trial, using the dose of IFN α of 20 MU/M².

2.7 Rationale

The current trial tests the safety and clinical effectiveness of the inclusion of personalized patient-specific immunotherapy in the clinical management of peritoneal surface malignancies

(including but not limited to peritoneal carcinomatosis of colorectal-appendiceal and mesothelioma origin), the disease characterized by a uniformly poor overall prognosis and managed with the combination of surgical cytoreduction, local and systemic chemotherapy, similar in all subtypes.

The tested combination immunotherapy will simultaneously target a) each patients' lymphocytes specific to unique tumor-associated antigens overexpressed on each patient tumors, and b) tumor microenvironment (tumor stroma and infiltrating cells) in order to mobilize host's immune responses against their own tumors and to counteract local immune suppression typical of the peritoneal cavity.

We expect to uniformly achieve this goal by:

- a) Immunizing each patient with his/her own polarized dendritic cells (α DC1s) loaded with their tumor material as the source of unique patient/tumor-specific antigens (rather than using a pre-determined synthetic antigen), in order to induce the most relevant pattern of immunity in each patient;
- b) Utilizing our recently-developed triple CKM regimen which targets peritoneal stromal cells and local inflammatory infiltrate (rather than tumor cells themselves) in order to condition the peritoneal environment and promote selective attraction of the desirable effector cells (CTLs, TH1 and NK cells), while eliminating the local attraction and suppressive functions of the undesirable immune cells (T_{reg} s and MDSCs).

We anticipate that such personalized immune therapy will provide a complementary, indirect, and therapeutic synergy with chemotherapy (which directly targets tumor cells), jointly resulting in delayed time to disease progression.

2.7.1 Rationale for intranodal and intradermal administration of α DC1 vaccines

The optimal route of DC administration has not been determined. Our recently completed trial in glioma patients used an intranodal (IN) route of vaccine delivery.⁴⁰ In the current trial, we would like to administer a portion of the vaccine via an intradermal (ID) route in order to facilitate additional prolonged stimulation of the immune system by slowly migrating DCs.

2.7.2 Rationale for the combination of α DC1 vaccine and the proposed chemokine-modulating regimen

Based on our preclinical observations that α DC1 vaccine induce high levels of two chemokine receptors, CCR5 and CXCR3 on tumor-specific CTLs³⁹ and the proposed combination of IFN α , TLR3 ligand and COX2 inhibitor selectively increase the tumor production of the chemokine ligands for these receptors CCR5 ligand: CCL5; and CXCR3 ligands: CXCL9 and CXCL10⁴², we expect that the **proposed combination will be able to promote tumor immune surveillance by a) inducing high numbers of tumor-specific CTLs (α DC1 component of treatment) and b) directing them to the tumor tissues (CKM component)**, thus establishing local immune surveillance within the peritoneal cavity and prolonging the time to disease recurrence.

3. PATIENT SELECTION

Consent will be obtained for this study on all eligible patients by the investigator or sub-investigators. No patient will be entered into this clinical trial without having signed a consent form. The research nurse coordinator or designee will screen the patients further, as per investigator/sub-investigator orders, to determine if they meet all the inclusion/exclusion criteria. If a recruited patient is excluded or resigns for any reason during the course of study, a new patient will be enrolled. However, such patients may continue to be followed and/or receive any available vaccine doses.

Candidates for this trial will have peritoneal surface malignancies and CRS + HIPEC is clinically indicated as the first line treatment. Due to the autologous nature of the vaccine, tumor tissue and the cells obtained from the leukapheresis procedure are required. Without those the vaccine cannot be manufactured and the patients are not eligible for this clinical study.

Surgical outcome of must be deemed able to undergo optimal CRS defined as CC-score of 0 or 1 based on post-surgical imaging. Cytoreduction is defined as the burden of residual disease nodules left at the end of surgery (CC-0: no visible disease; CC-1: residual tumor nodules \leq 2.5 mm in size; CC-2: residual tumor nodules 2.5 mm – 2.5 cm in size; CC-3: residual tumor nodules $>$ 2.5 cm in size).

Screening will occur after recovery from surgery to ensure they meet criteria for treatment.

3.1 Pre-surgery Eligibility

1. Histologically confirmed peritoneal surface malignancies, including but not limited to malignant peritoneal mesothelioma and peritoneal carcinomatosis (PC) from presumed appendiceal and colorectal primary tumors.
2. The following malignancies are ineligible for this study: low grade appendiceal and pseudomyxoma peritonei.
3. Clinically indicated for optimal CRS+HIPEC
4. At least 18 years of age
5. Able to understand and willing to sign a written informed consent document

3.2 Post-surgery Screening

3.2.1 Inclusion Criteria

1. Must have had HIPEC during surgery
2. Must have a CC score of 0
3. ECOG performance status of 0, 1 or 2
4. Able to swallow pills
5. Platelet \geq 75,000/ μ L
6. Hemoglobin \geq 9.0 g/dL
7. Hematocrit \geq 27.0%
8. WBC $>$ 2000/mm³
9. Creatinine $<$ 1.5 x institutional upper limit of normal (ULN), OR Creatinine clearance \geq 50

mL/min/1.73 m² for patients with creatinine levels greater than 1.5 x ULN

- 10. Total bilirubin \leq 1.5 x ULN
- 11. AST(SGOT) and ALT(SGPT) \leq 2.5 X ULN
- 12. Must be eligible for pheresis within 8 weeks of surgery
- 13. Availability of sufficient number of tumor cells for cryopreservation and subsequent vaccine production

